During the CRC visit women will also have one blood draw done (less than 25 cc's per draw; will take less than 10 minutes) by a CRC nurse and have their body composition measured by BodPod, waist circumference, and skinfold. R01 and R56: Blood will be centrifuged and aliquoted by a trained research technician using standard biohazard safety procedures. Samples will then be frozen at -80° C. Once all samples have been collected, they will be transported on dry ice to selected laboratories for analyses. The biomarkers selected for analysis (listed below) have been linked to fetal growth, metabolic syndrome and cardiovascular disease, which may be exacerbated in pregnancy due to high GWG or postpartum weight retention. The blood biomarker measurements that we will be assessing are as follows: Iron, CRP, Vitamin A, Vitamin D, Folate, Zinc, Selenium and Copper. Blood draws are being done for data collection purposes and study team has applied for an Institutional Biosafety Committee approval that was submitted on 12/14/15.

Women who are cleared for participation will be randomized into the intervention or control group. Once randomized, they will complete a series of paper based and online self-reported measures of their healthy eating [HE; Three Factor Eating Questionnaire-18], physical activity [PA; Leisure-Time Exercise Questionnaire], and weight [Pregnancy Weight Gain Attitude Scale], temperament [Rothbart Adult Temperament Questionnaire], psychological well-being [Center for Epidemiological Studies Depression Inventory, Body Areas Satisfaction Scale and Figure Rating Scale, State Trait Anxiety Inventory, Perceived Stress Scale], self-regulation of HE and PA, self-control [Tangney Self-Control Scale], sleep [Pittsburgh Sleep Quality Index], motivational determinants [self-efficacy, attitude, subjective norm, perceived control, intention, beliefs], and sociodemographics. Descriptions of the measures can be found in Appendix A. For complete list and schedule of these measures, please see Appendix B. These surveys were all completed as part of the Study 1 protocol with no issues by participants (CATS 00000122).

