Subjects will also complete trainings of the Remote Food Photography Method (RFPM) and My Fitness Pal for dietary intake, and the Breezing Device for metabolism. These measures and descriptions are included as uploaded materials. Women will also be sent-home with a waist-mounted activity monitor (i.e., Actigraph) and asked to wear it for the next 7 days, continuously except for showering and at bed time for an accurate assessment of their activity time (activity counts). They will also be asked to wear a wrist-worn activity monitor (e.g., Jawbone Up; looks like a bracelet) and asked to wear this non-stop for the next 7 days and not to take it off (it can be worn during showering and sleep) for a continuous assessment of activity and sleep patterns. The PI, [name], has used this activity monitoring protocol in previous research, including IRB 24174 Active MOMS and our Study 1 protocol (CATS 00000122). There are no risks associated with using activity monitors in pregnancy. Women will then be scheduled for their first intervention session for the following week and they will return their waist-mounted activity monitor to a study staff member. They will wear the wrist-worn monitor for the remainder of the study. They will be given a standard food scale and weight scale (Wi-Fi Fit Bit Aria) to take home for use in the intervention. If participant agrees to participate, they will be asked to weigh themselves daily until delivery. Urine samples will be collected weekly during the prenatal period to assess basal cortisol level as it relates to stress.

R01 and R56: Participants will be asked to collect voided urine overnight, starting from the time participant falls asleep and ending with the last collection being first morning void after waking for the day. We will provide 1 collection container for whole the whole study for storage of all urine. We will also provide a urine collection hat for easy collection. Participants will track time they went to bed, time of any/all collections overnight and time of first morning void.

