18.0 Subject Stipend and/or Travel Reimbursements

Reimbursement:

All participants will receive:

\$100 for the pre-intervention assessments

\$200 for the post-intervention assessments

Wi-Fi weight scale to keep upon completion of the study (\$125 value)

If the study is completed in its entirety an additional \$200

Free parking on PSU campus

Picture of baby after each scan

Those also randomized to the intervention will receive:

\$15 per month in merchandise gift-cards for self-monitoring x 6 months = \$90 total

A food scale (\$25 value)

Total of compensation in gifts and money: \$740

Additional compensation at the Postpartum period:

\$25 for completing the Remote Food Photography during the 3rd trimester

\$50 for your baby's measurements

\$50 for your postpartum onsite measurements

\$75 for the weekly measurements

Totaling \$200.

R56: The additional normal weight control subjects will receive up to \$300 in compensation for data collection only:

\$25 for each study visit (baseline, follow-up, and postpartum) for a total of up to \$75

\$5 per week for daily weighing, urine collection, and surveys for a total of up to \$200

A bonus \$25 for completing all visits and measures

Free parking on Penn State campus during your in-person visits

Free childcare during in-person visits to the Penn State campus (must schedule in advance)

Procedures will be followed for reporting payments to the University for tax purposes.

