energy expenditure [total LTEQ = (9 x strenuous) + (5 x moderate) + (3 x mild)]. Previous research using this measure has modified the quantification of exercise to include average minutes rather than metabolic equivalents across a week to better examine whether or not participants were meeting exercise guidelines (Courneya et al., 2004; Courneya, et al., 2007). Thus, outcomes can be quantified in MET equivalents or by multiplying reported values of strenuous, moderate, and mild physical activity (PA) by 15 to get total min/week for each type and then adding those values together to total min of weekly exercise.

- ii. Physical Activity (PA) Log: Women will be completing a daily PA log asking them series of questions: 'what time they put their activity monitor on and what time they took it off', 'if they were physically active that day'- if yes 'what activities they did', if it was a normal day in terms of their physical activity and if no, an 'explanation of why'.
- iii. Actigraph wGt3X-BTI: Women will be wearing the Actigraph monitor for 7 days during their free living immediately following their baseline appointment and again for 7 days immediately following their final appointment. Women will also be wearing the Actigraph for 3 weeks during the intervention phase of the study – the Actigraph is being counterbalanced with the UP Jawbone where half of the women will wear the Actigraph for the first two weeks of the intervention phase and the other half for the last two weeks of the intervention phase.
- iv. UP Jawbone: Women will be wearing the UP Jawbone for the entire six week intervention. UP will track how you sleep, move and eat so the women will be able to make smarter choices. Women will be wearing the UP Jawbone in counterbalance with the Actigraph wGt3X-BTI.

D. Personality Measures

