4	Perceived Stress Scale (PSS) 3 min 6 sec	10	REDCAP SURVEYS	P		X (P?)		--	P	
5	Rothbart Adult Temperament 3 min 4 sec	45	REDCAP SURVEYS	P ^a	--	--	--	--	--	--
6	Pregnancy Figure Rating Scale (PFRS) 1 min 27 sec	6	REDCAP SURVEYS		O			O	O	--

Survey #	Measure	# items	Data Collection	Pre (Onsite)	Pre (7-day)	Weekly	Biweekly	Monthly	Post (Onsite)	Post (7-day)
Dietary Intake										
1	RFPM	--	PHONE, APP	X	--	--		3 (2 weekday, 1 weekend at week Baseline, 16, 22, 28, 35 (post) weeks are gestational week)	X	--
2	MyFitnessPal	--	PHONE APP, WEBSITE	--	--	O (3-5 days/ week)	--	--	--	--
Resting Metabolic Rate										
1	Breezing Device	--	BREEZING DEVICE, PHONE APP	X	--	--	--	3 (2 weekday, 1 weekend at week Baseline, 16, 22, 28, 35(post) weeks are gestational week)	X	--
Notes. P = paper; O = online; DDE = double data entry. ^a Before Clinical Research Center Physical Exam.										

[figure not shown]
SCHEDULE OF ASSESSMENT FOR OBJECTIVE PA ASSESSMENTS

Measure	# of items	Data Collection	Pre (Onsite)	Pre (7-day)	Weekly	Biweekly	Monthly	Post (Onsite)	Post (7-day)
Actigraph Accelerometer	--	Enter in excel file sheet NOT IN REDCAP	--	X	--	--	X (1 week, at week Baseline, 16, 22, 28, 35(post)))	--	X
Up Jawbone Wrist Monitor	--	Phone App, Enter in excel file sheet NOT IN REDCAP	--	X (daily)	X (daily)	--	--	--	X (daily)
Aria Fitbit W-Fi	--	At home Website, Enter in excel file sheet	--	X (daily)	X (daily)	--	--	--	X (daily)
Standardized Scale	--	CRC/Noll Enter in excel file sheet	X	--	X (session)	--	--	X	--
Medical Record Data	--	REDCAP (DDE)	--	--	--	--	Monthly prenatal visits	--	--

HMZ SCHEDULE OF ASSESSMENT FOR OTHER PHYSICAL ASSESSMENTS

Measure	# of items	Location	Pre (Onsite)	Pre (7-day)	Weekly	Biweekly	Monthly	Post (Onsite)	Post (7-day)
BodPod	--	128 Noll	X	--	--	--	--	X	--
Blood	--	CRC	X	--	--	--	--	X	--
Cortisol (Urine)	--	CRC	X	--	X	--	--	X	--

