Appendix C. Baseline Assessment and Adaptive Step-Layout

Gestational Week	Study Week	Lesson #	Adaptation					
8	1		BASELINE ASSESSMENT (Onsite visit + home surveys and GWG/HE/PA monitoring)					
9	2	1	BASELINE INTERVENTION					
10	3	2	Education Modules [GWG, PA/HE, Self-Monitoring, Goal-Setting; Using guideline recommendations (GWG, HE, PA)]; Focus on health of baby/weekly “fun facts”					
11	4	3	Encouraged to get 150 min MVPA per week [to meet this goal, aiming to walk 10,000 steps/day and increase intensity (e.g., jogging/workout) as appropriate]					
12	5	4	GWG/PA/Self-Monitoring/Goal-Setting education delivered by PA instructor; HE counseling delivered by RD					
GWG Assessment and Decision Rules for Adapting Intervention								
13 (2 nd Tri)	6	5	Baseline Intervention +	STEP-UP 1: Active Learning I				
14	7	6		HE Active Learning: 4 Pearls Integrated into Cooking/Grocery Store Demo's: Reinforcing Messages + Recipe Booklet				
15	8	7		PA Active Learning: 1 st MVPA Session in Lab (combo treadmill, cycle, low impact aerobics, resistance exercises) in addition to 10,000 steps				
16	9	8		Self-Regulation Active Learning ^a : If-Then Action Plans (attach mental contrasting and implementation intentions to goal-setting)				
GWG Assessment and Decision Rules for Adapting Intervention								
17	10	9	Baseline Intervention +	Step-Up 1 +	STEP-UP 2: Active Learning II			
18	11	10			HE Active Learning: Portion Sizes and Containers			
19	12	11			PA Active Learning: 2 nd MVPA: Choice of Lab workout or walking with instructor + Workout Booklet (and 10,000 steps)			
20	13	12			Self-Regulation Active Learning ^b : Participants engage in charting their own HE/PA behaviors; use weight data to regulate eating and exercise behaviors; tie this process into action plans			
GWG Assessment and Decision Rules for Adapting Intervention								
21	14	13	Baseline Intervention +	Step-Up 1 +	Step-Up 2 +	STEP-UP 3: Active Learning III		
22	15	14				HE Active Learning: Grocery store receipt/pantry analysis; grocery store tour/activities; favorite recipe make-over		
23	16	15				PA Active Learning: 3 rd MVPA session: Choice of Lab (individual or group?) or at-home workout		
24	17	16				Self-Regulation Active Learning: We monitor HE/PA daily and provide feedback “check” (EMA-I)		
GWG Assessment and Decision Rules for Adapting Intervention								
25	18	17	Baseline Intervention +	Step-Up 1 +	Step-Up 2 +	Step-Up 3 +	STEP-UP 4: Active Learning IV	

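### Randomisation at Visit A comes before the 7-day baseline week, so the pre values of 14 of 18 repeated self-report scales and of home activity monitoring are post-randomisation, probably with the arm known

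*Combined protocol and SAP*

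**What the plan says.** Section 6.2 (Visit A) describes the clinical examination, blood draw and body composition, then randomises the women who are cleared, and then turns to the questionnaires: "Once randomized, they will complete a series of paper based and online self-reported measures of their healthy eating". The description of Visit C confirms that randomisation belongs to Visit A, since it repeats Visit A apart from randomisation and the medical history review.

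The same section then sends women home with a waist monitor and a wrist monitor for seven days. Appendix A agrees: "Women will be wearing the Actigraph monitor for 7 days during their free living immediately following their baseline appointment". On the next step, 6.2 says "Women will then be scheduled for their first intervention session for the following week" and, on equipment for use in the intervention, "They will be given a standard food scale and weight scale". Section 18.0 lists the food scale only under the heading "Those also randomized to the intervention will receive".

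Appendix B has two pre columns, one onsite and one for the following seven days. Most scales are in the second. A few onsite paper forms carry the footnote "Before Clinical Research Center Physical Exam". Appendix C describes study week 1 as "BASELINE ASSESSMENT (Onsite visit + home surveys and GWG/HE/PA monitoring" and places lesson 1 in week 2.

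No section says when a woman learns her arm.

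**The concern.** A baseline value is protected from the effect of allocation only if it is collected before allocation, or at least before the arm is known. Here most behavioural and psychosocial baselines come afterwards. A woman who knows that she will be coached on eating and exercise may answer differently, or move more, in her monitored week; a woman who knows that she is a control may do so too.

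Aim 1 hypothesises better eating, activity, psychosocial and behavioural outcomes in the intervention arm, and 8.2 estimates arm differences in change from pre to post. A baseline shift caused by allocation is subtracted from that difference. The outcomes concerned are secondary, but Aim 1 also sets out to test the randomisation and data-collection procedures, so the order could pass into the future RCT.

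**Working it through.** **1. The plan's sample size.** Section 8.1 needs 12 per group and allows 20% drop-out: 12/(1 - 0.20) = 15 per group, 30 in total. This reproduces. The point concerns these 30 women; the extra normal-weight controls are not randomised.

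**2. Count of scales (Appendix B).** There are 23 self-report rows. Four are pre-only (demographics, health history, clinic medical history, temperament) and one is the monitor wear log. That leaves 23 - 4 - 1 = 18 scales with pre and post values.

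- Pre value in the 7-day column: planned behaviour 4, self-regulation 2, self-control 1, self-efficacy 2, eating 1, leisure exercise 1, sleep 1, weight attitudes 1, figure rating 1 = 14.
- Pre value onsite: CES-D, STAI, BASS and PSS = 4.

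The baseline Actigraph, wrist monitor and home weights are also in the 7-day column. Fourteen is the minimum: it is 15 if PSS, which lacks the footnote, follows randomisation, and 18 if 6.2 is read literally.

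**3. A contradiction.** Section 6.2 lists CES-D, STAI, BASS and temperament among the measures completed after randomisation. Appendix B marks them as done before the physical exam, and clearance and randomisation follow that exam. Both cannot hold.

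**4. How much of a baseline shift reaches the estimate.** Assume that the shift affects the baseline value only and that time is fitted as a straight line with equally weighted points. The share entering the end-to-end change, with opposite sign, is

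(t̄ - t₁)(t_K - t₁) / Σ(t - t̄)²

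with baseline at week 8 and post at week 35 (Appendix C) and intermediate points from Appendix B.

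| Schedule | t̄ | Σ(t - t̄)² | Share | Bias at 0.3 SD shift |
|---|---|---|---|---|
| Two points: 8, 35 | 21.5 | 364.5 | 13.5 × 27/364.5 = 1.00 | 0.30 SD |
| Actigraph: 8, 16, 22, 28, 35 | 21.8 | 436.8 | 13.8 × 27/436.8 = 0.85 | 0.26 SD |
| Monthly scales: 8, 12, …, 32, 35 | 21.875 | 644.875 | 13.875 × 27/644.875 = 0.58 | 0.17 SD |
| Biweekly self-regulation: 8, 10, …, 34, 35 | 21.933 | 1092.93 | 13.933 × 27/1092.93 = 0.34 | 0.10 SD |

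A simulation with 12 per arm, correlation 0.5 and a 0.3 SD shift (20,000 runs) gave -0.31, -0.25, -0.18 and -0.10. If the model instead adjusts for baseline, the share is about the pre-post correlation ρ. With ρ assumed to be 0.3 to 0.7, the bias is 0.09 to 0.21 SD. A 0.1 SD shift gives one third of each figure.

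**5. Scale.** The standard error of a two-point change contrast at 12 per arm is √(2(1 - ρ)) × √(2/12): 0.48, 0.41 and 0.32 SD for ρ = 0.3, 0.5 and 0.7. At ρ = 0.5 the largest bias is 0.30/0.41, about 0.7 of a standard error.

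**The case against.** Harm requires the arm to be known, and no section says that it is. Section 6.2 speaks of women in general when it books the first session and hands out the food scale; read literally, every woman gets both and nothing is revealed. Section 18.0 is a compensation list, not a statement of who uses the equipment. This stands to the extent that disclosure is inferred. But in an unblinded behavioural trial that books intervention sessions at the randomisation visit, disclosure is the likelier reading, and the silence is itself a gap.

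A shift that persists to week 35 cancels in the present pre-to-post contrast, whereas an earlier baseline would leave it in the effect. That is correct, so step 4 is limited to a baseline-only shift. Moving randomisation protects the baseline; it does not remove reporting bias at follow-up. Even so, a contrast of arms as randomised should not subtract something that allocation produced.

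The shift size and ρ are assumptions, and 8.2 does not specify a linear time term. For daily data the share is smaller: about 0.2 for the wrist monitor, or 0.06 SD for a 0.3 SD shift. Planned-behaviour control beliefs are biweekly, so 0.34 applies to them rather than 0.58. Appendix A also describes a different Actigraph schedule within a six-week intervention, which does not fit the weeks behind the 0.85. These points narrow the illustration and leave the sequence unchanged.

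Section 6.2 refers to Appendix B for the schedule, so the CES-D, STAI and BASS conflict may be only wording; it still needs correcting. Finally, this is an estimation pilot, the future RCT is to be powered on gestational weight gain, and the values precede the first session. That limits the seriousness, but biased change estimates are a poor product for a pilot whose purpose is estimation.

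**Conclusion.** The concern holds. On the plan's own order, at least 14 of the 18 repeated self-report scales, and the baseline week of home monitoring, are collected after randomisation. That the arm was known is probable but not stated. The risk is a reaction to knowing the arm, not exposure to the sessions.

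The direction and size of any shift are unknown. Over the assumed range of -0.3 to +0.3 SD, the bias runs from nothing to 0.30 SD, depending on the outcome's schedule and the model. Unlike sampling error, it would not shrink with more women.

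Clinic weight, blood and body composition are described before the randomisation step, so the clinic anchor for gestational weight gain is not affected. This is a change that should be made for the secondary outcomes of Aim 1; it does not threaten the primary endpoint.

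**What to change.** - Randomise, or at least disclose the arm, only after the 7-day baseline week, when the waist monitor is returned. Move session booking and food-scale issue to that point, and define the same monitor-return contact for controls.
- Align 6.2 with Appendix B so that every baseline scale, including PSS, precedes randomisation, and state when the arm is disclosed. If only disclosure is delayed, every baseline scale should precede disclosure.
- In 8.2, fit the pre/post models with a common baseline mean across arms or with baseline as a covariate. Both rely on the new order.
- For women already entered under the present order, record the disclosure date and the dates of the scales, and adjust only for variables measured before randomisation, such as clinic weight and gestational week.

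The cost is one reordered step, one defined contact for controls, and edits to 6.2 and one sentence of 8.2. The sample size does not change, and intervention women need no extra visit because their first session is already a week later. The drawback is that session slots and arm-specific equipment are settled about a week later.

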2. Baseline + Active Learning 1: Condition 1 description + adding 4 pearls integrated into cooking/grocery store demos: reinforcing messages and recipe booklet. A registered dietitian will deliver these demonstrations with Safe Serve Certification in the Clinical Research Center kitchen in the Elmore Wing of Noll Laboratory. There will be 1 moderate to vigorous intensity physical activity session located in 223 Noll Laboratory with 5-min of introduction, 5-min of warm-up, 30-min of guided PA instruction lead by the intervention leader, and 5-min of cool-down. Women will have their choice to engage in physical activity via walking/light jogging on the treadmill, cycle ergometer, low impact guided aerobics, and resistance training (bands/5 and 10 pound weights); all activities following the USDHHS (2008) and ACOG (2015) national recommendations for regular moderate-intensity PA. The written scripts for these demonstrations and the forms to assess fidelity monitoring are attached in the documents section of CATS. For self-regulation, there will be If-Then action plans. The written scripts/handouts for these demonstrations are attached in the document section of CATS. The forms used to assess fidelity monitoring of these sessions are also attached in the documents section.
3. Baseline + Active Learning 2: Condition 1 description + the choice of a second 45-min physical activity session on site or walking with an instructor and will receive a workout booklet. Healthy eating active learning will include education and the use of portion size and containers. Self-regulation activities include charting healthy eating and physical activity behaviors and use weight data to regulate eating and exercise behaviors by using action plans. The written scripts/handouts for these demonstrations are attached in the document section of CATS. The forms used to assess fidelity monitoring of these sessions are also attached in the documents section
4. Baseline + Active Learning 3: Condition 1 description + grocery store receipt/pantry analysis; grocery store tour/activities; favorite recipe makeover, a third 45-minute physical activity session with the choice of coming on site or at home and we will provide feedback regarding their self-regulation/monitoring behaviors.

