5. Baseline + Active Learning 4: Condition 1 description + adding 1 meal replacement (lunch or dinner) for 7 days, a fourth physical activity session with the choice of on site or at home and a weekly text/call/email feedback and encouragement for self-regulation/monitoring. The meal will be frozen meals, packaged for the week and they will meet the recommended dietary guidelines for pregnant women for lunch or dinner. The written scripts/handouts for these demonstrations are attached in the document section of CATS. The forms used to assess fidelity monitoring of these sessions are also attached in the documents section
6. Baseline + Active Learning 5: Condition 1 description + adding 1 meal replacement (lunch or dinner) for 7 days, a fourth physical activity session with the choice of on site or at home and text/call/email feedback and encouragement for self-regulation/monitoring 3x/week. The meal will be frozen meals, packaged for the week and they will meet the recommended dietary guidelines for pregnant women for lunch or dinner. The written scripts/handouts for these demonstrations are attached in the document section of CATS. The forms used to assess fidelity monitoring of these sessions are also attached in the documents section

After the follow-up assessment at gestational week 35, the participants will be followed through delivery and up to 6- weeks postpartum.

During the exercise session, we will employ the same symptoms monitoring system that we used in Active MOMS IRB #24174 and CATS

Symptom Checklist	Pre	5-min	15-min	25-min	Post
Dizziness					
Nausea					
Headache					
Abdominal Pain/Pressure					
Cramping or contractions					
Chest pain					
Calf pain or swelling					
Fluid leakage (urine, amniotic, blood)					
Unusual change in fetal movement					

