00000122. A CRC nurse will be present for a portion of the exercise session to provide oversight to the subject monitoring during normal business hours. Trained fitness instructors with CPR training will be present at all times during the after-hours exercise sessions. If there should be a need for immediate medical care, assistance from the CRC would be solicited during normal business hours and after-hours, 911 would be called. A study staff member will also be present at all times during an exercise session. If immediate medical attention is needed, the study staff member will call 911, Penn State police and alert the PI. Subjects will be monitored by a trained study staff member at all times, and will be asked at pre-exercise, at 5-min, 15-min, 25-min, and post-exercise to report (a) standard rating of perceived exertion (Borg Scale) and (b) symptoms checklist (ACOG, 2015):

RPE

6	
7	very, very light
8	
9	very light
10	
11	light
12	
13	somewhat hard
14	
15	hard
16	
17	very hard
18	
19	very, very hard
20	

35. CK, Correa JB, Han H, et al. Validity of the Remote Food Photography Method (RFPM) for estimating energy and nutrient intake in near real-time. *Obesity*. Apr 2012;20(4):891-899.

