10.1 Periodic evaluation of data

Daily weight data will be collected for intervention monitoring. Weekly HE and PA behaviors, self-regulation, psychological well-being, motivational determinants of HE and PA, and weight behaviors will also be collected and used to inform the intervention counseling in the following week. Also, as described above, will also collect PA session data on symptoms monitoring at pre-exercise, 5-min, 15-min, 25-min, and post-exercise.

See attached protocol for unexpected or adverse events monitoring.

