11.0 Risks

This research does not involve more than minimal risk to the participants as defined in SOP HRP-001 "Minimal Risk is the probability and magnitude of harm or discomfort anticipated in the research that are not greater in and of themselves than those ordinarily encountered in daily life or during the performance of routine physical or psychological examinations or tests." Engaging in regular moderate-

intensity PA and eating a healthy diet are not high risk activities. The education, active learning, goal-setting, and self-monitoring procedures employed in this study do not place the participants at risk for harm. There are some minimal risks associated with engaging in physical activity (e.g., sore muscles, dizziness, etc) that are no greater than those ordinarily encountered in daily life or during the performance of routine activity. Women with obstetric and medical complications and/or who meet the ACOG (2015) criteria for a contraindication to exercise will be excluded from study participation. There are no known risks of a mother eating a healthy diet and engaging in PA to the fetus. Most epidemiological data and the USDHHS (2008) guidelines illustrate benefits to the mother and the fetus such as improved stamina during delivery, lower rates of emergency C-sections, and reduced complications during delivery among healthy mothers. CRC nurses will check in during the exercise sessions during normal business hours. Trained fitness instructors with CPR training will be present at all times during the after-hours exercise sessions. If there should be a need for immediate medical care, assistance from the CRC would be solicited during normal business hours and after-hours, 911 would be called. A study staff member will also be present at all times during an exercise session. If immediate medical attention is needed, the study staff member will call 911, Penn State police and alert the PI.

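### Unqualified statements that staff watch exercise sessions conflict with the at-home option for the third and fourth weekly sessions, so home-session symptoms may be under-captured

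*Combined protocol and SAP*

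**What the plan says.** On supervision, Section 6.2.1 (Visits B) states that "Subjects will be monitored by a trained study staff member at all times" and that RPE and a symptom checklist are taken before exercise, at 5, 15 and 25 minutes, and afterwards. Section 11.0 adds "A study staff member will also be present at all times during an exercise session", and the same sentence stands in Sections 6.2.1 and 16.4. In the safety plan, Section 10.1 says the study "will also collect PA session data on symptoms monitoring at pre-exercise, 5-min, 15-min, 25-min, and post-exercise". None of these statements makes an exception for location.

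On where sessions take place, the first added session (Active Learning 1) is in the laboratory. For the second (Active Learning 2) the woman has "the choice of a second 45-min physical activity session on site or walking with an instructor", so supervision is provided for either way. Active Learning 3 adds "a third 45-minute physical activity session with the choice of coming on site or at home". Active Learning 4 and 5 each include "a fourth physical activity session with the choice of on site or at home". Appendix C gives the same home choice for the third and fourth sessions.

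**The concern.** A third or fourth session done at home cannot meet the presence and monitoring statements as written, and the available text puts nothing in their place. This matters for two reasons.

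First, Section 11.0 describes the supervision of exercise sessions in support of a minimal-risk classification, so that description should be accurate.

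Second, Section 2.3 says the study is to establish the dosage of components before a randomized trial. Symptom data are then most useful if they are collected in the same way at each step-up level. Here the structured check covers every added session at the lower levels but may miss up to half of them at the top levels. The AE rate behind the Section 10.8 alert would rest partly on structured questioning and partly on what women volunteer.

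**Working it through.** The plan states no figure for this point, so the check sets the passages side by side and then counts the sessions affected.

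**1. Is there a home procedure in the available text?**
- Section 6.2.1 describes no checklist, RPE or staff contact tied to a home session. Remote contact at the top level is "text/call/email feedback and encouragement for self-regulation/monitoring 3x/week", which is not symptom capture.
- Appendix A: the daily physical activity log covers monitor wear times, whether and how the woman was active, and whether the day was normal, with an explanation if not. It has no symptom items.
- Appendix B lists no symptom form.
- Section 11.0: the steps for an event during exercise presuppose staff on site. They include positioning the participant, contacting the Clinical Research Center nearby, and a nurse or staff member completing the form and the AE log.

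**2. Share of added weekly sessions that may be at home** (steps cumulative, as in Appendix C)

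| Level | Added sessions per week | May be at home | Share | On site or with an instructor |
|---|---|---|---|---|
| Baseline | 0 | 0 | – | 0 |
| Active Learning 1 | 1 | 0 | 0% | 1 |
| Active Learning 2 | 2 | 0 | 0% | 2 |
| Active Learning 3 | 3 | 1 | 1/3 = 33% | 2 |
| Active Learning 4 and 5 | 4 | 2 | 2/4 = 50% | 2 |

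**3. Maximum count over pregnancy.** Inputs from Appendix C: the first to fourth sessions start at gestational weeks 13, 17, 21 and 25, and the last intervention week is 34. Sessions = last week − first week + 1, at one of each per week.
- First: 34 − 13 + 1 = 22. Second: 34 − 17 + 1 = 18. Third: 34 − 21 + 1 = 14. Fourth: 34 − 25 + 1 = 10.
- Total 22 + 18 + 14 + 10 = 64. Home-eligible 14 + 10 = 24, and 24/64 = 37.5%.
- If the last dosage is kept to week 40: 28 + 24 + 20 + 16 = 88. Home-eligible 20 + 16 = 36, and 36/88 = 40.9%.

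These are ceilings. They need a step-up at every decision and the home choice every time. Section 6.2.1 describes a two-week baseline level where Appendix C shows four weeks; that would move the start weeks but not the weekly shares in step 2.

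**4. What under-capture could do to the alert (illustration only).** Section 8.1 recruits 15 per group: 12/(1 − 0.20) = 15. The Section 10.8 threshold of 20% is then 0.20 × 15 = 3 women. The documents give neither an AE risk nor a capture rate, so both are assumed. With X ~ Binomial(15, risk × capture), P(X ≥ 3) is:

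| Assumed true risk | Capture 100% | Capture 75% | Capture 50% |
|---|---|---|---|
| 20% | 0.60 | 0.40 | 0.18 |
| 30% | 0.87 | 0.69 | 0.40 |

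The capture rate here applies to all AEs. Loss confined to home sessions would have a smaller effect. The table shows only the direction, and that a threshold of three women leaves little margin.

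**The case against.** The strongest reply is that this is loose wording, not a gap in safety data. The text around the presence statements (nurse, campus police, Clinical Research Center) reads as if written for on-site sessions, and the statements fail only if a woman chooses home. AEs are not tied to location: Section 10.2 defines them as any detrimental change, Section 11.0 has staff track them, Section 10.8 monitors rates in all participants, and Section 20.1 covers reported as well as observed harm.

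There are also several points of contact. Intervention women are seen weekly (Sections 6.3 and 10.4), the activity log has its explanation field, Appendix C adds daily monitoring of eating and activity with feedback from Step-Up 3, and prenatal records are accessed. Appendix D teaches exercise safety in week 9 and warning signs in week 25. Unsupervised activity is encouraged from the baseline level, so unobserved exercise is not peculiar to the top steps.

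Most of this stands, and it rules out three stronger readings that a reader might infer:
- That harms at home go uncounted, or have no route to the AE log. The provisions above give them one.
- That symptom capture falls in absolute terms as the dose rises. Sessions that must be on site or with an instructor go 0, 1, 2 and then stay at 2; only the share falls.
- That the loss sits at the doses the future trial will adopt. Section 6.1 says that trial will test a modified, optimized program.

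The reply does not remove the contradiction. No passage tells staff to ask about home-session symptoms at the weekly visit, so capture there depends largely on what the woman volunteers. Encouraged free-living activity also differs from a prescribed session that counts as intervention dose.

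**Conclusion.** The inconsistency holds: the presence and five-point monitoring statements carry no location limit, and the same protocol permits the third and fourth sessions at home with no symptom or RPE procedure in the available text. Up to 1 of 3 (Active Learning 3) and 2 of 4 (Active Learning 4 and 5) added weekly sessions are affected, with a ceiling of 24 of 64 to week 34.

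The supported consequence is possible under-capture of home-session symptoms, with ascertainment that differs by location and step-up level. Its size cannot be derived, because the documents give no uptake of the home choice, no AE risk and no capture rate. The session counts measure eligibility, not missed harm.

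The conclusion rests on the cumulative reading of Appendix C. It also rests on the available text: the uploaded session scripts and AE protocol, and the text between Sections 10.4 and 10.6, could not be checked, and a home procedure there cannot be excluded. Even if one exists, the statements in Sections 6.2.1, 11.0 and 16.4 would still need correcting.

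**What to change.** Reconcile Sections 6.2.1, 10.1, 11.0 and 16.4 with Appendix C, so that the staff-presence statements and the at-home option agree. Which clinical rule is right is for the investigators and is not decided here.

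If the home option stays:
- Limit the presence and monitoring statements to on-site sessions.
- Have the woman complete the same symptom checklist and RPE sheet for each home session.
- Review the sheet at the existing weekly face-to-face session.
- Log events under the AE criteria already used on site, including the minor-event exclusion in Section 10.2 and the moderate-to-severe threshold in Section 11.0.
- Record session location and report it descriptively. With about 15 women who choose their own location, a comparison of AE rates by location could not be interpreted.

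The cost is a small amendment: an existing form, a few minutes at a visit already scheduled, and no new staff. The drawbacks are that self-completed data are less complete than staff-observed data, participants carry a small added burden, and AE counts may rise slightly.
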